8.0 Adverse Events

8.1 Definitions

Adverse Event

An adverse event (AE) is any untoward medical occurrence that develops or worsens in severity during the course of the study, whether or not it has a causal relationship to the study treatment. Concurrent illnesses or injuries should be regarded as AEs. Abnormal results of diagnostic procedures are considered AEs if the abnormality:

- results in study withdrawal
- is associated with a serious adverse event
- is associated with clinical signs or symptoms
- leads to additional treatment or to further diagnostic tests
- is considered by the investigator to be of clinical significance

Serious Adverse Event

Adverse events are classified as serious or non-serious. A *serious adverse event (SAE)* is any AE that is:

- fatal
- life-threatening
- requires or prolongs hospital stay
- results in persistent or significant disability or incapacity
- a congenital anomaly or birth defect
- an important medical event

Important medical events are those that may not be immediately life threatening, but are clearly of major clinical significance. They may jeopardize the subject, and may require intervention to prevent one of the other serious outcomes noted above. For example, drug overdose or abuse, a seizure that did not result in in-patient hospitalization or intensive treatment of bronchospasm in an emergency department would typically be considered serious.

All adverse events that do not meet any of the criteria for serious should be regarded as *non-serious adverse events*.

Adverse Event Reporting Period

The study period during which adverse events must be reported is normally defined as the period from the initiation of any study procedures to the end of the study treatment follow-up. For this study, the study treatment follow-up is defined as within 90 days following the last administration of study treatment.

Preexisting Condition

A preexisting condition is one that is present at the start of the study. A preexisting condition should be recorded as an adverse event if the frequency, intensity, or the character of the condition worsens during the study period (e.g. if behavior worsens).

General Physical Examination Findings

At screening, any clinically significant abnormality should be recorded as a preexisting condition. At the end of the study, any new clinically significant findings/abnormalities that meet the definition of an adverse event must also be recorded and documented as an AE.

Post-study Adverse Event

All unresolved AEs should be followed by the investigator until the events are resolved, until the events are otherwise stable or the subject is lost to follow-up. At the last scheduled visit, the investigator should instruct each subject to report any subsequent event(s) that the subject, or the subject's personal physician, believes might reasonably be related to participation in this study.

Abnormal Laboratory Values

A clinical laboratory abnormality should be documented as an AE if any one of the following conditions is met:

- The laboratory abnormality is not otherwise refuted by a repeat test to confirm the abnormality
- The abnormality suggests a disease and/or organ toxicity
- The abnormality is of a degree that requires active management; e.g. change of dose, discontinuation of the investigational product, more frequent follow-up assessments, further diagnostic investigation, etc.

Hospitalization, Prolonged Hospitalization or Surgery

Any AE that results in hospitalization or prolonged hospitalization should be documented and reported as a SAE unless specifically instructed otherwise in this protocol. Any condition responsible for surgery should be documented as an AE if the condition meets the criteria for an AE. Neither the condition, hospitalization, prolonged hospitalization, nor surgery are reported as an AE in the following circumstances:

- Hospitalization or prolonged hospitalization for diagnostic or elective surgical procedures for a preexisting condition. Surgery should not be reported as an outcome of an AE if the purpose of the surgery was elective or diagnostic and the outcome was uneventful.
- Hospitalization or prolonged hospitalization required to allow efficacy measurement for the study.
- Hospitalization or prolonged hospitalization for therapy of the target disease of the study, unless it is a worsening or increase in frequency of hospital admissions as judged by the clinical investigator.

8.2 Recording of Adverse Events

At each contact with the subject, the investigator must seek information on adverse events by specific questioning and, as appropriate, by examination. Information on all AEs should be recorded immediately in the source document, and also in the appropriate adverse event module of the case report form (CRF). All clearly related signs, symptoms, and abnormal diagnostic procedures results should be recorded in the source document and grouped under one diagnosis when possible.

All AEs occurring during the study period must be recorded. The clinical course of each event should be followed until resolution, stabilization, or until it has been determined that the study treatment or participation is not the cause. Serious adverse events that are still ongoing at the end of the study period must be followed up to determine the final outcome.

8.3 Reporting Procedures for Adverse and Serious Adverse Events

All adverse and SAEs will be reported in accordance with FDA and local IRB requirements. In addition, any SAE will be reported to NuvOx and the Sponsor by the Investigator within 24 hours after becoming apparent.

All SAEs that meet the IRB's UPIRTSO requirements must be submitted to the IRB within 10 working days. All other SAEs will be submitted to the IRB at continuing review. Copies of each report and documentation of IRB notification and receipt will be kept in the Clinical Investigator's binder.

8.4 Data Safety and Monitoring Plan

All safety data will be reviewed by the Medical Monitor after each patient and after the completion of each cohort. All moderate and severe safety signals that are unanticipated and probably or definitely related to the investigational product will be discussed with the Sponsor and NuVox prior to enrolling additional subjects. A Data Safety and Monitoring Board will not be appointed.

8.5 Medical Monitor

A Medical Monitor (MM) will be selected. The MM will be a licensed physician who is familiar with cardiovascular disease and stroke. The MM will review the data collected after each patient and after each dose level and will provide an opinion to the investigator as to whether it is advisable to proceed with dose escalation as described in Section 5.3.3. As part of the review, the MM will review all AEs and assure that any SAEs have been reported appropriately.

8.6 Risks and Benefits

Risks may include pain from IV placement, hypotension, reversible inflammatory changes in the lungs, nausea, vomiting, drowsiness, dizziness, fever, headache, reduced or elevated blood pressure, blanching of the gums, and allergy to soy or eggs. There may be unanticipated adverse events or outcomes. It is anticipated that oxygen delivery to ischemic areas of the brain may improve thereby changing clinical signs. It is unclear as to whether this might result in reduced cerebral tissue loss or any improvement in outcome following stroke. There may be no benefit to subjects.

8.7 Risk Mitigation

All subjects will be observed in a unit accustomed to treating patients with stroke. Customary clinical care will be provided by the patient's treating physician. No standard treatments will be withheld as a result of participation in the study.

Adverse events will be actively sought through the study at multiple time points. All AEs will be recorded and evaluated for severity and relatedness and followed to resolution. A MM will be appointed to review safety issues as described in Section 8.5. Repeated measurement of clinical, ECG, and laboratory data have been included to detect important safety signals. Careful assessment of all AEs, especially those that are probably or definitely related to the investigational product, will be conducted.

9.0 Data Collection

9.1 Data Collection and Storage

All source data will be recorded on Case Report Forms (CRFs) as described in Sections 9.4 and 9.5. CRFs will be placed in the subjects' study file and stored in a

locked file cabinet or on password protected or encrypted electronic media. All data will be appropriately monitored by the sponsor to assure data quality and integrity. Electronic data capture will not be used in this study.

9.2 Confidentiality

Information about study subjects will be kept confidential and managed according to the requirements of the Health Information Portability and Accountability Act (HIPAA). Those regulations require a signed subject authorization informing the subject of the following:

- The personal health information (PHI) to be collected from subjects in this study
- Who will have access to that information and why
- Who will use or disclose that information
- To whom the data may be disclosed and the reasons for this disclosure
- The rights of a research subject to revoke their authorization for use of their PHI

In the event that a subject revokes authorization to collect or use PHI, the investigator, by regulation, retains the ability to use all information collected prior to the revocation of subject authorization. For subjects that have revoked authorization to collect or use PHI, attempts should be made to obtain permission to collect at least vital status (i.e. that the subject is alive) at the end of their scheduled study period.

9.3 Study Monitoring and Data Queries

The investigator is required to permit the Sponsor to monitor the study data, including all communications with the IRB, the manufacturer, all source documents, CRFs, pharmacy records, and any other pertinent information. Monitoring visits will be scheduled at a time that is convenient for both the monitor and the investigator. The monitor will provide a written report to the investigator within one month after the conclusion of the monitoring visit.

9.4 Source Documents

Source data is all information, original records of clinical findings, observations, or other activities in a clinical trial necessary for the reconstruction and evaluation of the trial. Source data are contained in source documents. Examples of these original documents, and data records include: hospital records, clinical and office charts, laboratory notes, memoranda, subjects' diaries or evaluation checklists, pharmacy dispensing records, recorded data from automated instruments, copies or transcriptions certified after verification as being accurate and complete, photographic negatives, microfilm or magnetic media, x-rays, subject files, and records kept at the pharmacy, at the laboratories, and at medico-technical departments involved in the clinical trial.

9.5 Case Report Forms

The study CRF is the primary data collection instrument for the study. All data requested on the CRF must be recorded. All missing data must be explained. If a

space on the CRF is left blank because the procedure was not done or the question was not asked, write “N/D”. If the item is not applicable to the individual case, write “N/A”. All entries should be printed legibly in black ink. If any entry error has been made, to correct such an error, draw a single straight line through the incorrect entry and enter the correct data above it. All such changes must be initialed and dated. DO NOT ERASE OR WHITE OUT ERRORS. For clarification of illegible or uncertain entries, print the clarification above the item, then initial and date it.

9.6 Study Auditing

The investigator will permit study-related monitoring, audits, and inspections by the IRB, the study Sponsor, government regulatory bodies, and UAMS compliance groups of all study related documents (e.g. source documents, regulatory documents, pharmacy documents, data collection instruments, study data etc.). The investigator will ensure the capability for inspections of applicable study-related facilities (e.g. pharmacy, diagnostic laboratory, etc.).

Participation as an investigator in this study implies acceptance of potential inspection by government regulatory authorities and applicable compliance offices. FDA may choose to inspect the study records as indicated in 21 CFR 312.58.

9.7 Record Retention

It is the investigator’s responsibility to retain study essential documents for 2 years following the date a marketing application is approved for the drug for the indication for which it is being investigated (21 CFR 312.62). These documents should be retained for a longer period if required by an agreement with the funding entity or the supplier of the investigational agent. In such an instance, it is the responsibility of the funding entity or supplier of the investigational product to inform the investigator/institution as to when these documents no longer need to be retained.

10.0 Data Analysis Plan

10.1 Sample Size

This is a Phase I study. No sample size estimates were done.

10.2 Clinical Data

Demographic data will be presented as the mean \pm SD (range) for normally distributed data (median \pm interquartile range for non-normal data).

Clinical data includes vital signs and pulse oximetry (pre- and post-intervention). Pre- and post-intervention data will be grouped and examined for differences using a two-sided t-test or ANOVA, as appropriate. Pre- and post- laboratory data will be compared in a similar manner. ECGs will be read by a board-certified cardiologist and clinically significant changes will be described.

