3.1 Study Design

This study is a randomized, placebo controlled, blinded escalating dose study designed to determine the MTD and adverse events possibly related to intravenous administration of DDFPe. At each of three dose levels (0.05, 0.10, 0.17 mL/kg) six subjects will receive DDFPe and two will receive placebo.

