5.3.3 Maximum Tolerated Dose

The algorithm for determining the MTD is as follows:

- Up to six subjects and two controls will be enrolled at each dose level constituting each cohort. Subjects will be evaluated for four hours after receiving the last of the three doses and again at discharge from the hospital or one week later, whichever is sooner.
- DLT is previously defined in [Section 5.3.2](#).
- If no DLTs are observed in a patient at Post-Dose #3 of DDFPe or placebo the Medical Monitor may allow progression to the next patient.

- After all 8 subjects have been enrolled in a cohort, the Medical Monitor will review the data. A decision as to whether the study may proceed to the next cohort will be made.
- If a total of two or fewer subjects in an 8 subject cohort experience a DLT, escalation to the next cohort may proceed if approved by the Medical Monitor. If three or more DLTs were observed, the Medical Monitor may consult with the Research Pharmacist to determine if the observed DLTs occurred in subjects who received DDFPe or placebo. If any of the DLTs were observed in the subjects receiving placebo, the Medical Monitor may allow the study to proceed as long as two or fewer subjects with DLTs received DDFPe.
- If three or more subjects who received DDFPe in an 8 subject cohort experience a DLT, the MTD will be determined to have been exceeded and further enrollment in the cohort as well as dose escalation will stop. The dose administered to the previous cohort will be considered to be the MTD.
- Subjects who withdraw from the study for reasons other than a DLT may be replaced.
- The Medical Monitor will review all safety data for each patient and cohort and must grant approval before proceeding to the next patient and/or cohort.
- Exploration of lower dose levels intermediate to a level previously shown to be well tolerated may be considered. In addition to reducing the dose, this might include reducing the number of doses, increasing the time between doses, and/or altering the infusion time.
- The dose exploration will be complete when either: (1) the MTD has been defined or (2) when no MTD has been reached but six subjects and two controls have been treated at the last cohort level approved by the Medical Monitor.

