7.1 Usual Care Provided by Treating Physician

Customary (routine) care for patients suffering a stroke will be offered as would be the case had the patient not enrolled in the trial. This may include physiological monitoring, medical procedures, drug therapy (including tPA), respiratory support, and ancillary or accessory care. Routine care will be directed by the patient's treating physician. If the treating physician believes that it is no longer in the best interest for the patient to continue in the study, he/she will contact the investigator and immediately stop all study-related procedures.

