7.5.9 Laboratory Studies

All subjects will have the following laboratory tests collected prior to receiving DDFPe:

- Complete Blood Count
- Electrolytes (Na, K, Cl₂)
- BUN
- Creatinine
- LFTs (AST, ALT, Total Bilirubin, Direct Bilirubin, Albumin)
- Calcium
- Glucose

It is anticipated that many of these tests will be done as part of the subjects' routine care. These tests will provide baseline values prior to administration of DDFPe for later comparison with post-dosing test results. The results of these tests may or may not be available prior to dosing with DDFPe. None of the tests would exclude a subject from participating in the study.

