7.6 Day 1: Study Procedures

After documentation that the subject passed the screening procedures and meets all Inclusion and Exclusion criteria, study personnel will check to assure that a patent intravenous catheter is in place for infusion of the DDFPe. The catheter should be used solely for infusion of DDFPe and compatible intravenous fluids during the study intervention period (from the initiation of Dose #1 to after the Dose #3 infusion is complete).

Dose #1: DDFPe will be ordered from the pharmacy and prepared as previously described. The time that the infusion begins will be recorded. The drug or placebo will be infused over 5-10 minutes. At the end of the infusion, the time will again be recorded. Vital signs and pulse oximetry will be monitored. Measurements will be recorded every 15 minutes. The subject will be observed for any signs of adverse events for 90 minutes after the completion of the infusion.

Dose # 2: Any new concomitant medications will be recorded. The second dose of DDFPe or placebo will be administered as previously described over 5-10 minutes. Times will be recorded at the beginning and end of the infusion as before. Vital signs and pulse oximetry will be monitored. Measurements will be recorded every 15 minutes. The NIHSS will be repeated within 60 minutes after the end of the DDFPe infusion. The subject will be observed for any signs of adverse events for 90 minutes after the completion of the infusion.

Dose #3: Any new concomitant medications will be recorded. The third dose of DDFPe or placebo will be administered as previously described over 5-10 minutes. Times will be recorded at the beginning and end of the infusion as before. Vital signs and pulse oximetry will be monitored. Measurements will be recorded every 15 minutes. The NIHSS will be repeated within 60 minutes after the end of the DDFPe

infusion. The subject will be observed for any signs of adverse events for 90 minutes after the completion of the infusion.

Vitals should be taken at all scheduled time points (i.e. every 15 minutes); however, deviations from scheduled times will not be considered protocol deviations. The exact date and time of each measurement will be recorded on the CRF.

Post-Dose #3: Approximately 4 ± 1 hours after the end of Dose #3, the following observations will be made:

- Concomitant medications administered after Dose #3
- A brief physical examination
- Vital signs (BP, HR, RR)
- Pulse oximeter measurement
- NIHSS
- ECG

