7.7 Day 4: Study Procedures

All subjects will be contacted to assess AEs. If the subject is still hospitalized, any significant change in condition will be recorded as a possible AE and assessed by the investigator. All AEs will be graded (mild, moderate, severe), assessed for relatedness (not related, possibly related, probably related, definitely related), and followed to resolution as described in Section 8.0.

In the event that the subject has been discharged from the hospital before Day 4, subjects or their LAR will be contacted by telephone. AEs will be assessed and followed as described above.

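### Section 10.2 names only a pre/post comparison for vital signs, pulse oximetry and laboratory values, and no DDFPe–placebo contrast, although each cohort is randomised 6:2 against placebo

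*Combined protocol and SAP*

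**What the plan says.** Section 3.1 describes a randomised, blinded, placebo-controlled escalation in which, at each of three dose levels, "six subjects will receive DDFPe and two will receive placebo".

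Section 10.2 covers vital signs and pulse oximetry before and after the intervention: "Pre- and post-intervention data will be grouped and examined for differences using a two-sided t-test or ANOVA, as appropriate". It then adds: "Pre- and post- laboratory data will be compared in a similar manner". Arm, dose and placebo are not mentioned in that section. Pairing, the significance level, the ANOVA factors and the post-dose time point are not stated either.

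Section 10.3 says that safety data will be reported and that the MTD follows the rules given earlier. The one DDFPe–placebo comparison named in Section 10 is in 10.4. It is exploratory and concerns NIHSS only.

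Section 7.1 leaves routine stroke care to the treating physician: "This may include physiological monitoring, medical procedures, drug therapy (including tPA), respiratory support, and ancillary or accessory care".

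**The concern.** Subjects are enrolled within 12 hours of stroke onset and are under active treatment while the post-dose readings are taken. Blood pressure, heart rate, saturation and laboratory values can move over those hours for reasons unrelated to DDFPe. A pre/post difference counts all of that movement as if it followed from the study drug.

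The error can run either way. Drift alone can give a small p-value, and a real drug effect opposed by an equal drift shows as no change. The six placebo subjects are there to tell these cases apart, and 10.2 gives them no stated role. At stake is whether the reported mean changes, which would inform Phase 2, can be attributed to DDFPe.

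**Working it through.** **Inputs from the documents.** Section 3.1: 3 cohorts × (6 + 2) = 24 subjects, of whom 3 × 6 = 18 receive DDFPe and 3 × 2 = 6 placebo. This matches the maximum of 24 in the Study Summary. Section 10.1 reports no sample size calculation, so there is no planned power or effect size to reproduce.

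**Assumptions (not in the documents).** Two-sided alpha 0.05; normally distributed changes with equal SD; no drug effect; the same background drift δ in both arms, of 0.25, 0.5 or 0.75 SD of change.

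**1. What each contrast estimates.** Let θ be the DDFPe effect on mean change.
- Pre/post in DDFPe subjects: θ + δ.
- Pre/post in all 24: (18/24)θ + δ = 0.75θ + δ.
- DDFPe minus placebo: (θ + δ) − δ = θ.

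**2. Rejection rate of a paired pre/post test when θ = 0.** The statistic is noncentral t with n − 1 degrees of freedom and noncentrality δ√n. For n = 18 and δ = 0.5, the noncentrality is 0.5 × 4.243 = 2.12, which gives 51.6%.

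| Subjects in the test | δ = 0.25 | δ = 0.5 | δ = 0.75 |
|---|---|---|---|
| One dose group, n = 6 | 8% | 17% | 32% |
| All DDFPe, n = 18 | 17% | 52% | 85% |
| All subjects, n = 24 | 22% | 65% | 94% |
| DDFPe v placebo, 18 v 6 | 5% | 5% | 5% |

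**3. If ANOVA with arm and time is used.** In simulation (18 v 6, 100,000 runs) the time main effect, with arms weighted equally, rejects 17%, 53% or 86% of the time at the three drifts. The arm-by-time interaction stays at 5%. The term that is read decides the answer, and 10.2 does not name it.

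**4. If the t-test is unpaired.** With an assumed pre/post correlation of 0.3, 0.5 or 0.7 and a drift of 0.5 SD, the simulated rejection rate is 39%, 25% or 9% for n = 18, and 52%, 36% or 14% for n = 24. With no drift it is 2.2%, 0.8% or 0.1% for n = 18, so the test does not hold its nominal 5% even then.

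**5. Precision of the between-arm contrast.** The 95% half-width is t × √(1/n₁ + 1/n₂), in SD of change.
- 18 v 6: t(22) × √(1/18 + 1/6) = 0.98. With a cohort term, t(20) gives the same to two decimals.
- 18 v 6, baseline-adjusted by simulation: about 0.80 to 0.92 for correlations of 0.3 to 0.7.
- One cohort, 6 v 2: about 2.0.
- Power for 18 v 6 is 17% at 0.5 SD; 80% needs about 1.38 SD.

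**6. Which post-dose value.** Section 7.6 schedules an assessment about 4 ± 1 "hours after the end of Dose #3, the following observations will be made", that is 180 to 300 minutes. Section 1.4 gives a terminal half-life of 81 to 99.5 minutes, from bolus doses of 0.15 to 0.35 mL/kg. The assessment therefore falls 180/99.5 = 1.8 to 300/81 = 3.7 half-lives after the last dose. Roughly 29% down to 8% of the terminal-phase level then remains, after a rapid initial decline. A single reading at that point could miss short-lived changes around the infusions. Section 7.6 and Appendix 4 already have vital signs recorded every 15 minutes.

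**The case against.** The strongest reply is that 10.2 is unspecific rather than wrong. A single pre/post contrast needs only a t-test, so the mention of ANOVA and of grouped data may point to dose levels and placebo as groups. That stands: a reader might infer that 10.2 excludes an arm comparison, and the text does not say so. The consequence is therefore conditional on the pre/post contrast being the one tested. ANOVA could equally refer to the repeated 15-minute readings, and wording that allows either analysis prespecifies neither.

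Section 7.5.9 says of the baseline laboratory tests: "These tests will provide baseline values prior to administration of DDFPe for later comparison with post-dosing test results". One might take this as confirming an uncontrolled analysis. It does not, because any change-from-baseline analysis uses baselines in this way.

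The illustrated rates rest on assumed drifts. If the data are grouped by dose, so that each test has 6 subjects, the rates are far lower than for 18 or 24. Both points stand.

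Finally, the primary objective is the MTD, the secondary objective is the frequency and severity of adverse events, and six placebo subjects give little precision. This limits the weight of the point. Small numbers, however, are a reason to report estimates with intervals. They are not a reason to test an uncontrolled difference.

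**Conclusion.** The point holds as a gap in a supporting safety analysis. The only difference that 10.2 names for these variables is pre versus post, and that difference cannot isolate DDFPe when subjects are also changing with the stroke and its treatment. With no drug effect, a common drift of 0.5 SD makes a paired test reject 17%, 52% or 65% of the time for n = 6, 18 or 24, against 5% for the randomised contrast. These figures depend on the assumed alpha, drift and pairing.

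Two stronger readings are not supported. The first is that the trial never compares DDFPe with placebo; Section 10.4 does so for NIHSS. The second is that the dose decision is compromised. Section 5.3.3 counts events by treatment received ("If three or more subjects who received DDFPe in an 8 subject cohort experience a DLT", the MTD is deemed exceeded), and individual abnormal values are still caught by the DLT and adverse event rules. Ascending doses and relatedness grading also bear on attribution, but neither gives a randomised comparison of mean change in these variables.

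**What to change.** Rewrite 10.2 before unblinding:

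- **Main analysis:** baseline-adjusted difference in change, pooled DDFPe versus pooled placebo, with a cohort term. Report it with a 95% confidence interval and make no significance claims.
- **By dose:** show each dose level and placebo descriptively, noting that only 2 of the 6 placebo subjects are concurrent with any one dose.
- **Laboratory values:** use the scheduled Post-Dose #3 sample. First reconcile its window, which is 4 ± 1 hours in Section 7.6 but about 4 to 6 hours in Section 5.3.2 and Appendix 4.
- **Vital signs and oximetry:** prespecify per-subject summaries of the 15-minute readings during and after dosing, for example the mean and the most extreme change from baseline, rather than the single Post-Dose #3 value. Fix the time window and the handling of missing readings, because an extreme depends on how many readings there are.
- **Pre/post differences:** keep as description.
- **Section 10.3:** add one sentence that adverse events and DLTs are tabulated by the same arms.

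The cost is wording only, with no new visits, tests or data. The downside is imprecision: about ±0.98 SD of change for 18 v 6 before adjustment, wider if the trial stops early (about ±2.0 SD after one cohort), and 17% power at 0.5 SD. Moderate effects will still be missed, and the report should say so.
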